**Table 4.2: Analysis Time Windows of Bayley Scales, HFMSE, Development Milestones and Pulmonary Exam – Cohort 3 Patients**

Scheduled Visit	Nominal Days (Study Day)	Acceptable Analysis Window in Study Days (Min Day – Max Day)
Baseline	-	< 1
Month 1	30	1 to 38
Day 44	44	39 to 49
Month 2	60	50 to 66
Day 72	72	67 to 77
Month 3	90	78 to 104
Month 4	120	105 to 134
Month 5	150	135 to 164
Month 6	180	165 to 194
Month 7	210	195 to 224
Month 8	240	225 to 254
Month 9	270	255 to 284
Month 10	300	285 to 314
Month 11	330	315 to 344
Month 12	360	345 to 374

Scheduled Visit	Nominal Days (Study Day)	Acceptable Analysis Window in Study Days (Min Day – Max Day)
Month 13	390	375 to 404
Month 14	420	405 to 434
Month 15	450	≥435

Safety data, such as laboratory results, vital signs, ECGs, and physical exams will be assessed by date and study day. For change from baseline analyses the value associated with the scheduled visit will be used. For summaries of shifts from baseline and potentially significant values all values will be considered for these analyses. Baseline for safety measures will be defined as the latest value before Day 1.

The efficacy data of this study will be compared to the data from the PNCR network. The analysis visit of PNCR will be based on the visit month defined in the PNCR dataset.

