time variable. Age at baseline will be used as a covariate. The probability of the ability to stand alone over time will be estimated using Kaplan-Meier methods. A Cox regression model will be used to obtain the hazard ratio with 95% CI for AVXS-101 Dose B to the data from PNCR. In this analysis, patients will be censored at the date of their End of Study visit.

All of the efficacy analyses stated above may be repeated using the ECAS as a sensitivity analysis, in the event the ECAS contains a subset of patients of the ITT Set.

If necessary, an additional set of sensitivity analyses may be conducted to include patients who demonstrated the developmental milestone of standing alone (Bayley-III, Gross Motor Subtest #40) which occurred after but within 3 months of the upper bound of the Month 12 visit window (day 374) due to COVID-19 disruptions.

In the first sensitivity analysis, the proportion of patients  $\geq$  6 months and  $<$  24 months of age at time of dosing that achieve the developmental milestone at any post-baseline visit (considering the expanded 3-month window) will be summarized overall and by dose. The corresponding p-value from a Fisher's exact test will be computed for the comparison between AVXS-101 Dose B and PNCR data. The summary and statistical analysis will be conducted using the ITT Set. The difference in the proportions between AVXS-101 and PNCR will be summarized and the exact 95% CIs will be provided accordingly.

In the second sensitivity analysis, the time from dosing to achieving the ability to stand alone will be summarized for patients overall and by dose in the ITT Set. The study day will be used as the time variable. Age at baseline will be used as a covariate. The probability of the ability to stand alone over time will be estimated using Kaplan-Meier methods. A Cox regression model will be used to obtain the hazard ratio with 95% CI for AVXS-101 Dose B and PNCR. In this analysis, patients who demonstrated the developmental milestone within the expanded 3-month window after Month 12 will be censored at the last attended visit prior to when the Month 12 visit was scheduled to occur.

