## 8.2. Secondary Efficacy Endpoint and Analyses

### 8.2.1. Proportion of patients that achieve ability to walk alone at any post-Baseline visit up to 12 Months

The developmental milestone walks alone as assessed by Bayley-III Gross Motor Subtest #43 will be assessed at the scheduled visits in accord with the Schedule of Assessments. The developmental milestone achievement of each patient in the study is based on the video evidence reviewed and confirmed by an independent central reviewer, as specified in SAP Section 6.4.3. The proportion of patients  $\geq$  6 months and  $<$  24 months and the proportion of patients  $\geq$  24 and  $<$  60 months at time of dosing who achieve the ability to walk alone up to 12 months will be summarized separately. The summaries will be done by dose and overall.

For the summary of each age group, the data from the historical dataset of PNCR network will also be included by the matched age group and analysis visits. The PNCR dataset evaluated the ability to walk alone per HFMSE item #20. PNCR patients with an HFMSE item #20 score of 2 at either the Baseline visit or at any post-Baseline visit within 12 months of Baseline will be considered to have achieved the developmental milestone. The HFMSE will not be started until patients reach 24 months of age; however, the Bayley-III will be assessed at Screening and all study visits. All patients who are able to walk alone at any post-baseline visit up to Month 12 will be classified as responders. All other patients will be classified as non-responders.

The corresponding p-value from Fisher's exact test will be computed for the comparison between AVXS-101 Dose B and PNCR data for each age group. The summary and statistical analysis will be done using the ITT Set. In each age group, the actual proportions as well as the difference of the proportions between two data sources will be summarized and the exact 95% CI will be provided accordingly.

For each age group, the time to achieving ability to walk alone will be summarized for patients overall and by dose using the ITT Set. The study day will be used as the time variable. Age at baseline will be used as covariate. A Cox regression model will be used to obtain the hazard ratio with 95% CI of AVXS-101 to the data from PNCR.

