All efficacy analyses stated above may also be performed using the ECAS as a sensitivity analysis in the event the ECAS contains a subset of patients of the ITT Set. Additionally, a sensitivity analysis will be performed for patients aged  $\geq$  24 and  $<$  60 months at time of dosing using the Sensitivity PNCR group. This sensitivity analysis will be based on the ITT Set and separately using the ECAS in the event the ECAS contains a subset of patients of the ITT Set.

If necessary, an additional set of sensitivity analyses may be conducted to include patients in the  $\geq$  6 months and  $<$  24 months group who demonstrated the developmental milestone of walking alone which occurred after but within 3 months of the upper bound of the Month 12 visit window (day 374) due to COVID-19 disruptions.

In the first sensitivity analysis, the proportion of patients that achieve the developmental milestone at any post-baseline visit (considering the expanded 3-month window) will be summarized overall and by dose. The corresponding p-value from a Fisher's exact test will be

computed for the comparison between AVXS-101 Dose B and PNCR data. The summary and statistical analysis will be conducted using the ITT Set. The difference in the proportions between AVXS-101 and PNCR will be summarized and the exact 95% CIs will be provided accordingly.

In the second sensitivity analysis, the time from dosing to achieving the ability to walk alone will be summarized for patients overall and by dose in the ITT Set. The study day will be used as the time variable. Age at baseline will be used as a covariate. The probability of the ability to walk alone over time will be estimated using Kaplan-Meier methods. A Cox regression model will be used to obtain the hazard ratio with 95% CI for AVXS-101 Dose B and PNCR. In this analysis, patients who demonstrated the milestone within the expanded 3-month window after Month 12 will be censored at the last attended visit prior to when the Month 12 visit was scheduled to occur.

Final

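### The COVID-19 time-to-event sensitivity analysis censors the late achievers it is meant to include, and its day-374 bound is not in the Dose B window table

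*SAP*

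**What the plan says.** SAP 8.1.1 opens the COVID-19 set with this purpose: "If necessary, an additional set of sensitivity analyses may be conducted to include patients who demonstrated the developmental milestone of standing alone". The children meant are those whose milestone came later than, but "within 3 months of the upper bound of the Month 12 visit window (day 374) due to COVID-19 disruptions". Two analyses follow.

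- The first is a proportion with a Fisher test of Dose B against PNCR. Late achievers are responders.
- The second is a Kaplan-Meier and Cox analysis in the ITT Set, with age at baseline as covariate. Here "patients who demonstrated the developmental milestone within the expanded 3-month window after Month 12 will be censored at the last attended visit prior to" the date on which Month 12 was due.

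SAP 8.2.1 repeats the pair for walking in the 6 to <24 month group: "patients who demonstrated the milestone within the expanded 3-month window after Month 12 will be censored at the last attended visit" before Month 12 was due. The supporting time-to-event analysis of standing in 8.1.1 has a different rule: "In this analysis, patients will be censored at the date of their End of Study visit".

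The windows are in SAP 6.5. Table 4.1 (Cohorts 1 and 2) starts Month 12 at day 345 and gives no upper limit. Table 4.2 (Cohort 3) gives days 345 to 374. SAP 6.1 restricts PNCR comparisons to Dose B, which is Cohort 2.

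**The concern.** There are two problems.

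**The censoring rule.** The second analysis does the opposite of what the set is introduced for. It names only the children who later achieve the milestone and takes them out of the risk set before Month 12. Censoring time is therefore chosen by the later outcome, and follow-up without a demonstrated milestone is thrown away. The supporting analysis of standing, which runs to End of Study, can already count a late achievement; the sensitivity analysis is the one that removes it.

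**The day-374 bound.** The tests concern Dose B, but the bound belongs to Cohort 3. Two programmers could classify the same delayed Dose B visit differently, so it is unclear whether such a visit counts in the Dose B standing and walking proportions.

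**Working it through.** **1. Where day 374 comes from.** Month 12 is nominally day 360, and 360 + 14 = 374, the upper limit in Table 4.2. It cannot be obtained from Table 4.1. With the SAP's 30-day month (SAP 1.1, defined there for age and assumed here for the window), the extended window is days 375 to 374 + 90 = 464. Under Table 4.1 all of these days are already Month 12 for Dose B.

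**2. Which reading the other sections favour.** SAP 4.1 and 4.2 and Protocol 14.6.2.1 define the endpoints up to the 12-month visit. Protocol Table 7, footnote 4, makes Month 12 the End of Study visit for Cohorts 1 and 2. SAP 7.1 tabulates Dose A and B completions more than 30 days late, that is after day 390. These favour counting a delayed final visit in the primary analysis, in which case the first COVID-19 analysis adds no Dose B child. Sections 8.1.1 and 8.2.1 imply that such a visit does not count.

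**3. What the censoring rule does.** The documents give no event times, so all of the following are assumed.

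- PNCR: 51 children, 7 events, 44 censored at day 360.
- Treated: 12 children, 8 on-time events at days 60, 120, 180, 210, 240, 270, 300 and 330; 1, 2 or 3 late achievers at day 420; the rest censored at day 360.
- Cox model with Efron ties, without the age covariate.

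As written there are 8 events however many children achieve late. The proportion analysis of the same set gives 9/12, 10/12 or 11/12 (75.0%, 83.3%, 91.7%).

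| PNCR event days | Last visit before Month 12 | HR, all censored at day 360 | HR as written, 1 / 2 / 3 late |
|---|---|---|---|
| 60, 120, 180, 180, 270, 360, 360 | 330 | 7.03 (95% CI 2.52 to 19.65) | 7.29 / 7.64 / 8.15 |
| same | 300 | 7.03 | 7.40 / 7.91 / 8.68 |
| 60, 120, 180, 180, 270, 270, 270 | 330 | 6.54 | 6.54 / 6.54 / 6.54 |
| same | 300 | 6.54 | 6.64 / 6.76 / 6.91 |

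The mechanism is the risk set. At day 360 there are 12 − 8 = 4 treated children at risk under common censoring, but 4 − 3 = 1 as written with three late achievers. PNCR events on that day are then set against fewer event-free treated children. If no event follows the censoring day, no risk set changes and neither does the hazard ratio.

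Kaplan-Meier with last visit day 330 stays at 66.7%. With last visit day 300 and three late achievers, survival is 5/12 after seven events, two children remain at risk at day 330, and 1 − (5/12)(1/2) = 79.2%. With one or two late achievers it is 68.8% or 72.2%.

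**4. What one reclassified child could do.** Two-sided Fisher, 12 against 51, using the control counts in SAP 5.6.1:

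- Standing (7/51): 4/12 gives p = 0.197 and 5/12 gives p = 0.041.
- Walking (5/51): 4/12 gives p = 0.058 and 5/12 gives p = 0.016.

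At the planned rates, P(≤4 of 12) is 0.00007 for standing (85%) and 0.057 for walking (60%).

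**The case against.** **The pair may be a bracket.** Late achievers are successes in one analysis and not achieved by Month 12 in the other. This is a reasonable design, but the SAP does not state it, and a clean lower bound would censor everyone without an on-time event on the same day.

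**Late achievements are not lost.** A reader might infer that they vanish from the report. They do not: the first analysis counts them, overall and by dose. The defect is confined to the time-to-event analysis.

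**The rule need not inflate the effect.** A reader might infer that it systematically favours treatment. With last visit day 330, the whole gap comes from placing two PNCR events at day 360. With all seven by day 270 it is zero, and with last visit day 300 it is about 1 to 6% (6.64 to 6.91 against 6.54). Seven PNCR events within 360 days is itself an assumption, because SAP 5.6.1 attaches no 12-month limit to the 7/51.

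**Day 374 is right for Cohort 3**, and the sentence that uses it names no dose. That stands, but the tests in the set are for Dose B only.

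**The two problems partly exclude each other.** If Table 4.1 governs, the set has little reason to run for Dose B; if day 374 governs, Table 4.1 lacks a bound. That also stands, and it is why one stated rule is needed.

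**Conclusion.** The point holds and is minor. On the text alone, the second COVID-19 analysis contradicts the purpose of its set for both milestones, makes censoring depend on a later outcome, and is neither inclusive nor a clean conservative bound. The day-374 bound conflicts with the window table for Dose B.

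The numerical effect is small and rests on assumed event times: from no change to about 16% in the hazard ratio with last visit day 330 (8.15/7.03), well inside the confidence interval. The set is optional, and the documents record no Dose B milestone after day 374. Nothing here shows that the primary standing conclusion is at risk; at the planned 85% the borderline counts are very unlikely.

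One further inference should be avoided: that treated-only events after the last PNCR time leave the Cox hazard ratio unchanged. This is so without covariates (7.03 either way above), but the SAP adjusts for age at baseline. In a simulation with assumed uniform ages (200 draws; PNCR 6 to 36 months, treated 6 to 24), three late events changed the adjusted ratio by factors of roughly 0.8 to 1.2.

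**What to change.** **(a) Second COVID-19 analysis, standing and walking.** Count late achievers as events on the achievement day and censor non-achievers at their last assessment. Print numbers at risk and do not interpret the Kaplan-Meier curve past day 374. Once on-time children are censored only delayed children remain, and in the illustration the curve jumps to 100% at day 420. If a conservative version is intended, say so and censor all children without an on-time event at one common day. Do not add a statement that late events leave the hazard ratio unchanged.

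**(b) Delayed Month 12 visit, Cohorts 1 and 2.** State one rule so that Table 4.1 agrees with 8.1.1 and 8.2.1. In choosing it, note that "The analysis visit of PNCR will be based on the visit month defined in the PNCR dataset", so a day cap on treated children alone could create a mismatch. Report the Dose B proportions with and without milestones first shown after day 374.

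The cost is a few lines of SAP text and one extra row per milestone table, with no new data. SAP 2.2.2 records that Dose B has already been analysed, so the clarification and both sets of results must be marked as specified after that analysis.

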#### **8.1.2. Change from Baseline in HFMSE at the 12 Month study visit for patients $\geq$ 24 months and $<$ 60 months of age at time of dosing**

The baseline, post-baseline, and change from baseline values in HFMSE will be summarized for patients overall and by dose. The summary and primary statistical analysis will be conducted using the ITT Set, and will be repeated using the PP Set as a sensitivity analysis. The patient data from the Primary PNCR group will also be included in the descriptive summary and analyses by the matched age group and analysis visits. The change from baseline to 12-month visit will be analyzed using a mixed model with repeated measurement (MMRM). The model will include the change from baseline as the dependent variable, fixed effect of cohort (AVXS-101 and PNCR), visit, and covariates of baseline HFMSE and age at baseline, and interactions of cohort\*age at baseline, baseline HFMSE\*visit, baseline HFMSE\*cohort, and cohort\*visit. A compound symmetry covariance structure will be assumed initially to model the within-patient errors; however, if compound symmetry results non-convergence, the variance component will be used. The unadjusted means, least squares (LS) means, differences between LS means, a 95% 2-sided CIs for each difference and the p-values from model effects will be reported for each scheduled visit.

A sensitivity analysis may be performed using the ECAS, in the event the ECAS contains a subset of patients of the ITT Set.

A sensitivity analysis will also be performed using the Sensitivity PNCR group and will be based on the ITT Set. This analysis may be repeated using the ECAS, in the event the ECAS contains a subset of patients of the ITT Set.

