#### **14.6.2.2. Primary Efficacy Endpoint: patients $\geq$ 24 months and $<$ 60 months at time of dosing**

The primary endpoint is the change from baseline in HFMSE for patients  $\geq$  24 months and  $<$  60 months of age at time dosing.

The primary efficacy analysis performed amongst patients aged between 24 months and  $<$  60 months of age at time of dosing will be the change from baseline in HFMSE at the 12-month study visit using a two-sample ANOVA at significance level of 0.05 (2-sided). A 95% confidence interval will be computed.

The primary analyses will be based on the Full Analysis Set for patients  $\geq$  24 months of age and  $<$  60 months of age at the time of dosing.

A sensitivity analysis will be conducted by repeating each primary efficacy analysis on the Efficacy Completers Analysis Set for patients  $\geq$  24 months of age and  $<$  60 months of age at the time of dosing.

A supportive analysis will be conducted by repeating the analysis of the primary efficacy endpoint for patients  $\geq$  24 months of age and  $<$  60 months of age considering data through the 15-month visit.

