## 2. PURPOSE

The purpose of this statistical analysis plan (SAP) is to ensure that the data listings, summary tables and figures which will be produced, and the statistical methodologies that will be used, are complete and appropriate to allow valid conclusions regarding the study objectives. The SAP was drafted with respect to the AVXS-101-CL-102 protocol version 8.0, incorporating amendment 7, dated 17 June 2019 entitled, *Phase I, Open-Label, Dose Comparison Study of AVXS-101 for Sitting but Non-ambulatory Patients with Spinal Muscular Atrophy*.

This SAP supersedes the statistical considerations identified in the protocol; where considerations are substantially different, they will be so identified.

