The primary efficacy endpoint will be the change in HFMSE in treated patients who are  $\geq$  24 months and  $<$  60 months of age at time of dosing. Twenty-four (24) children aged  $\geq$  24 months and  $<$  60 months will be enrolled, with twelve (12) children receiving Dose B and twelve (12) children receiving Dose C. Change in HFMSE score at 12 months will be compared with a cohort of eligibility-matched patients from the PNCR natural history study of SMA; this comparison will be conducted for Dose B only. Based upon a review of eligibility-matched patients from the PNCR dataset, a mean change of -1.33 points (standard deviation = 4.32 points) in the HFMS is seen at 12 months from baseline among patients aged 2-5 years at first evaluation with 3 copies of *SMN2*. However, the primary endpoint for this cohort is HFMSE, not HFMS. As such, the comparison to PNCR will utilize HFMSE. Among patients in this PNCR cohort, a mean change of -1.13 points (standard deviation=4.90) was seen in HFMSE, in line with other publications describing disease progression in SMA type 2 and 3 patients. It is expected to observe a mean increase of 8 points from baseline on the HFMSE in AVXS-101 treated patients with equivalent variance. Based upon these assumptions, twelve patients aged  $\geq$  24 and  $<$  60 months at enrollment will have  $>$  90% power to detect a significant difference with  $\alpha = 0.05$  when compared to patient-level data available from the PNCR dataset using a two-sample Analysis of Variance (ANOVA).

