## 5.6. PNCR Population-Matched Control Population

A population-matched control cohort will be drawn from the PNCR Natural History dataset. The PNCR is a large natural history study developed from a cohort of 337 patients with any form of spinal muscular atrophy followed at 3 large, internationally recognized tertiary medical centers with significant expertise in the management of SMA (Harvard University/Boston Children's Hospital, Columbia University and the University of Pennsylvania/Children's Hospital of Philadelphia).

Previously identified patients with any form of SMA, of any age, followed in PNCR site clinics and newly diagnosed patients were enrolled. All eligible patients were offered participation. Study visits were scheduled at baseline and at 2, 4, 6, 9, and 12 months and every 6 months thereafter. The SMA standard of care guidelines published in 2007 were used as a basis for providing uniform care among the study sites.

For purposes of this study, sitting (for SMA-II) was defined as being able to sit independently for > 10 seconds, and walking alone was defined as having scored 2 points on item #20 of the HFMSE at any time. All patients with SMA type 2 or 3 who provided sufficient records and follow-up for evaluation and met the basic entry criteria for the two cohorts of the AVXS-101-CL-102 study (3 copies of *SMN2*, symptom onset before 12 months of age and baseline and follow-up visits within the age criteria for the study) were considered for possible inclusion in the natural history comparison dataset. The *SMN2* modifier mutation (c.859G>C) described by Prior and colleagues (Prior et al., 2009) was not assessed in the PNCR study cohort.

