### 5.6.1. Primary analyses vs. PNCR

For the cohort of patients  $\geq$  6 months and  $<$  24 months of age, patient-level data from a cohort of 51 patients drawn from the PNCR Network natural history study of SMA will serve as a “population-matched” control cohort. This comparison cohort encompasses all 51 patients enrolled in the PNCR study who met the criteria of having SMA Types 2 or 3, 3 copies of *SMN2* and symptom onset before 12 months of age and had at least one visit at or before 36 months of age. Of this cohort, 7/51 (14%) of the natural history cohort attained the ability to stand alone (defined as achieving a score of 2 on item #19 of the HFMSE). 5/51 (10%) attained the ability to walk alone (defined as achieving a score of 2 on item #20 of the HFMSE).

For the cohort of patients between 24 and  $<$  60 months of age, patient-level data from a cohort of 15 patients drawn from the PNCR Network natural history study of SMA will serve as a “population-matched” control cohort for the primary analysis. This comparison cohort encompasses all 15 patients enrolled in the PNCR study who met the criteria of having SMA Types 2 or 3, 3 copies of *SMN2*, symptom onset before 12 months of age, diagnosis before 24 months of age and unable to stand or walk at enrollment (baseline visit) and who received a HFMSE evaluation between 24 and 60 months of age (“baseline”), and a follow-up evaluation

(HFMS or HFMSE) performed between 12 and 14 months following that baseline evaluation. It is stated in the protocol that among the patients in this cohort, a mean change of -1.33 points (Standard deviation=4.32) was seen in HFMS. However, the primary endpoint for this cohort is HFMSE, not HFMS. As such, the comparison to PNCR will utilize HFMSE. Among patients in this PNCR cohort, a mean change of -1.13 points (Standard deviation=4.90) was seen in HFMSE, in line with other publications describing disease progression in SMA type 2 and 3 patients (Kaufman et al 2012, Mercuri et al 2016). From this point forward, this PNCR comparator group of 15 patients will be referred to as the “Primary PNCR” group.

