## 6. GENERAL ASPECTS FOR STATISTICAL ANALYSIS

### 6.1. General Methods

In general, descriptive statistical methods will be used to summarize the data from this study. Hypothesis testing will be performed for the efficacy endpoints based upon the predetermined sample sizes. Unless stated otherwise, the term “descriptive statistics” refers to number of patients (n), mean, median, standard deviation, minimum, and maximum for continuous data and frequencies and percentages for categorical data. Unless noted otherwise, the data will be sorted first by dose (Dose A, then Dose B, then Dose C), age group, patient number, and then by date within each patient number.

Unless noted otherwise, all safety tables will be summarized using the SS, by the actual dose received and by age group.

All descriptive statistics of efficacy tables will be summarized by the assigned dose and age group. The efficacy analyses will be performed to compare with the efficacy endpoints of patients assigned to AVXS-101 and patients drawn from a widely (peer-reviewed) published natural history dataset collected by the PNCR network; comparisons to the PNCR data will be conducted for Dose B only. Efficacy data for Dose A and Dose C will only be summarized descriptively and will not be compared to the PNCR data.

Efficacy analyses will be conducted on the ITT or ECAS as specified within each section, with analyses on the ECAS produced only if the ECAS contains a subset of patients of the ITT. Since the FAS and the ITT Set include the same patients (SAP Section 5.3), the ITT Set is used to represent the efficacy analyses by the FAS stated in the protocol.

Unless specified otherwise, all statistical testing and confidence intervals (CI) will be 2-sided and will be performed using an alpha level of 0.05. No adjustments for multiple comparisons will be made.

All statistical analyses will be conducted with the SAS® software package version 9.4 or higher.

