Section 5.5 was updated to clarify the PNCR control group for the older patient cohort consisted of 15 patients, not 12 patients; to clarify that the PNCR control group for the younger cohort may have demonstrated the milestones of interest at any point, not at or before turning 36 months of age; to include the sensitivity analysis for the older patient cohort using a different group of 15 PNCR patients.

Section 6.1 was updated to state that no adjustments for multiple comparisons would be made.

Section 6.5 was updated to define the visit windows for Cohort 3 patients, and to include rules for remapping of efficacy data for PNCR patients which have data missing at the Baseline visit.

Section 7.1 was updated to include a summary table for patients who discontinued due to AE, and to clarify that a listing of major protocol deviations would be produced; to indicate that the number (%) of patients in the PP Set would be summarized.

Section 7.2 was updated to clarify which demographic characteristics would be summarized for the PNCR populations.

Section 7.3 was updated to indicate the table of SMA medical history should be based on the FAS.

Section 7.4.2 was updated to include a listing of AEs for patients who did not follow the protocol-prescribed taper for prednisolone.

Section 8.1.1 was updated to remove the sample SAS code; to clarify that patients in the PNCR group who achieved the milestone at either the Baseline visit or at a post-Baseline visit within 12 months of Baseline would be considered to have met the milestone; to indicate that the analysis of the primary endpoint will be repeated using the PP Set as a sensitivity analysis.

Section 8.1.2 was updated to remove the sample SAS code, and to include a sensitivity analysis based on the Sensitivity PNCR group; to indicate that the analysis of the primary endpoint will be repeated using the PP Set as a sensitivity analysis.

Section 8.2.1 was updated to remove the reference to sample SAS code; to include a sensitivity analysis based on the Sensitivity PNCR group; to clarify that patients in the PNCR group who achieved the milestone at either the Baseline visit or at a post-Baseline visit within 12 months of Baseline would be considered to have met the milestone.

Section 8.3.1 was updated to remove the sample SAS code; the text related to the comparison to PNCR data for this endpoint was removed as Bayley Scale scores are not available in the PNCR dataset.

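### The older cohort's primary HFMSE test at Month 12 assumes one variance for all visits, and the visible SAP plans no Month 12 comparison with PNCR that is free of that assumption

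*SAP*

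**What the plan says.** SAP Section 8.1.2 analyses change from baseline in HFMSE with an MMRM. It has terms for cohort, visit, baseline HFMSE, age and several interactions, and reports a difference, interval and p-value at each visit. On the covariance it says: "compound symmetry covariance structure will be assumed initially to model the within-patient errors; however, if compound symmetry results non-convergence, the variance component will be used". Repeats on the PP Set, the ECAS and the Sensitivity PNCR group change the patients or the controls, not the model.

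Protocol Section 14.6.2.2 has a different primary analysis: "the change from baseline in HFMSE at the 12-month study visit using a two-sample ANOVA at significance level of 0.05 (2-sided"). SAP Section 2 settles which governs: "This SAP supersedes the statistical considerations identified in the protocol", adding that substantial differences will be identified. Yet SAP Section 3.7 still claims more than 90% power "when compared to patient-level data available from the PNCR dataset using a two-sample Analysis of Variance (ANOVA").

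The other HFMSE analyses for this age group are a responder test at any visit (8.4.1), an average over Months 1 to 12 (8.4.2), and a comparison of Months 1-6 with Months 7-12 in treated children (8.4.3).

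On spread, SAP Section 5.6.1 reports that "a mean change of -1.13 points (Standard deviation=4.90) was seen in HFMSE" at about 12 months. No SD of HFMSE change is given for any other visit. Descriptive summaries are planned by visit; under Section 6.1 the term "refers to number of patients (n), mean, median, standard deviation, minimum, and maximum for continuous data". Treated children are assessed monthly. For PNCR, "Study visits were scheduled at baseline and at 2, 4, 6, 9, and 12 months".

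**The concern.** Both the chosen covariance structure and its fallback have a single variance. If variance component means independent errors, there is one variance; if it means a random patient intercept, it is compound symmetry again. The fallback is triggered only by non-convergence, so poor fit does not trigger it.

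Change from baseline can spread out as follow-up lengthens. If it does, the tighter early visits pull the pooled variance below the true Month 12 variance, and the Month 12 standard error is too small. The interval for the older cohort's primary endpoint is then too narrow, and a null or small effect is called significant too often. A Month 12 ANOVA does not pool over visits, but the visible SAP does not keep it even as a check.

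Section 8.4.3 has a separate fault. Each child contributes both an early and a late mean, but the listed ANCOVA terms include no patient effect, so the two means are treated as independent.

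**Working it through.** **1. The plan's power.** Inputs: 12 treated and 15 Primary PNCR children; expected change +8 against -1.13; SD 4.90 (SAP 3.7 and 5.6.1). Difference = 8 + 1.13 = 9.13. SE = 4.90 × sqrt(1/12 + 1/15) = 1.90. Noncentrality = 9.13/1.90 = 4.81 on 25 df, giving power of 99.6%. The stated figure of more than 90% is correct.

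**2. What the model pools.** Full data give 12 × 12 = 144 treated rows and 15 × 5 = 75 PNCR rows, 219 in all. The estimable mean model has 12 visit means, 5 cohort differences at shared visits, 12 baseline-by-visit slopes and 3 further terms: 32 parameters and 187 residual df. One variance is estimated from all 219 rows and applied at Month 12.

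**3. Type I error under assumed growth.** The documents give no SD by visit, so growth is an assumption. A share g of the Month 12 variance comes from child-specific slopes, with the Month 12 SD fixed at 4.90. The implied Month 1 to Month 12 SD ratio is sqrt(1 - g + g/144). Null trials were simulated and the SAP mean model fitted by REML with compound symmetry.

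| g | SD ratio | MMRM type I error | Model SE / true SE |
|---|---|---|---|
| 0% | 1.00 | 4.9-6.5% | 1.97 / 1.95-2.00 |
| 25% | 0.87 | 7.4-9.9% | 1.81 / 1.96-2.04 |
| 48% | 0.72 | 9.9-11.4% | 1.65-1.66 / 1.94-2.03 |
| 67% | 0.58 | 12.1-15.2% | 1.50-1.51 / 1.94-2.02 |

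The ranges span several simulation settings; Monte Carlo error is about 0.4 to 0.9 points. The Month 12 ANOVA stayed at 4.0-5.9%. An unstructured MMRM on the five shared visits with Kenward-Roger df gave 4.7-5.8%. With falling variance, the SAP model was conservative (3.1%).

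**4. Degrees of freedom.** The SAP text names no df method. It may be in programming documents: the SAP's change log notes that "Section 8.1.2 was updated to remove the sample SAS code", and Section 16 points to separate documentation. It is not the cause. At 67% growth, Kenward-Roger df give 12.4-13.8%, against 13.3-15.2% with 187 df in the same runs.

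**5. Interval width at 67% growth.** Reported half-width: 1.50 × 1.97 = 2.96. With the true SE of about 2.0 it is 2.0 × 1.97 = 3.94, and a Month 12 ANCOVA gives 4.05. The SE shortfall is 1 - 1.50/2.0 = 25%. An observed difference between about 3 and 4 points would change status. One of 9.13 would not, since 9.13 - 4.05 = 5.08 is above zero.

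**6. Section 8.4.3.** With n children, equal variances s² and residual correlation r between a child's two means, the true variance of the period difference is 2s²(1 - r)/n. The ANCOVA uses 2s²/n, so its SE is too large by 1/sqrt(1 - r): 1.15 at r = 0.25, 1.41 at 0.5, 2.24 at 0.8. Simulated type I error with 12 children is about 2.8%, 1.1-1.3% and 0.03-0.06%; a paired analysis gives 4.8-5.1%.

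**The case against.** **Compound symmetry is defensible with so few children.** An unstructured matrix over 12 visits has 12 × 13/2 = 78 parameters for 27 children. This stands, and it is why the MMRM should remain primary and the alternatives be sensitivity analyses on five visits.

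**The Month 12 ANOVA follows from the planned by-visit n, mean and SD.** True, but no planned output presents it as a test. The ANCOVA and the visit-specific model cannot be recovered from those figures.

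**The switch from ANOVA to MMRM may be explained elsewhere.** The text of SAP Section 14, on changes from the protocol, is not shown. A reader might infer that the change is undisclosed or that no ANOVA is kept anywhere; the documents do not support that, and the claim is limited to the visible SAP.

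**The harm is hypothetical.** This also stands. A reader might infer that the primary test has a false-positive rate of 13% or even 20%. Such rates need strong assumed growth (about 20% arises only with growth at 92% of the Month 12 variance), and the documents neither show nor exclude growth. The study is Phase 1, uses external controls and makes no multiplicity adjustment.

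**The by-visit SDs might seem to settle the matter.** They cannot do so reliably. PNCR has no Month 1 visit, so the Month 1 to Month 12 ratio rests on 12 treated children. Assuming a correlation of 0.85, the SE of its log is about sqrt((1 - 0.85²)/11) = 0.16, a 95% factor of about 1.4. Ratios of 1.00 and 0.87 cannot be told apart.

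**Section 8.4.3 is secondary and errs conservatively** when r is positive. Agreed; the factor also ignores the SAP's weights. The model is still wrong for paired data.

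**Conclusion.** The gap is in the plan's text: one variance for all visits, a fallback with the same assumption, and no other Month 12 comparison with PNCR in the visible SAP. Its consequence depends on a variance pattern that the documents do not give. With constant variance there is little harm. With 25% growth, type I error is about 7 to 10%; with 67% it is about 12 to 15%, and the interval is roughly a quarter too narrow. These figures assume normal errors, linear child-specific slopes, complete visits and a Month 12 SD of 4.90. Adjustment for baseline and age may shrink that SD, which would scale the widths but not the error rates.

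The stated power is correct. What is exposed is the precision claimed for the effect, and any conclusion resting on a difference of a few points. The fault in 8.4.3 is separate and makes that comparison too cautious when a child's two means are positively correlated.

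**What to change.** Keep the MMRM as primary and state its df method. Add two labelled Month 12 sensitivity analyses, reported beside it whatever they show:

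- (a) the protocol's two-sample ANOVA, and an ANCOVA with baseline HFMSE and age;
- (b) an MMRM on the shared visits (2, 4, 6, 9, 12) with unstructured covariance and Kenward-Roger df. If it does not converge, use heterogeneous compound symmetry, noting that this reached 7.1% type I error in one simulated missing-data case (12 against 17 children).

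State how re-mapped PNCR visits are handled. In the SAP 6.5 example they fall at Months 2, 5 and 8, so that child has no Month 12 value and drops out of (a). State also that Dose B data had already been analysed (SAP 2.2.2) and that the ANOVA was already in the protocol.

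Do not make the choice of interval depend on a width comparison. A rule that switched when the primary interval was more than 10% narrower than the ANCOVA's would fire in about 21 to 31% of trials with constant variance, and in only 56 to 59% at 25% growth.

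In 8.4.3, analyse the within-child difference or add a patient random effect.

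The cost is one SAP paragraph and a few lines of code, with no new data. A wider interval may appear beside the primary one: with constant variance the half-widths are about 3.9 for the MMRM and 4.05 for the ANCOVA. Power at 9.13 points is about 99.6% for the ANOVA and 98.8% for the unstructured MMRM (395 of 400 simulated trials). If three PNCR children lack Month 12, the half-width is about 4.3 for the ANCOVA and 4.1 for the unstructured MMRM.
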